8.1.2 Secondary Endpoints

- Percentage of subjects who become amenorrheic after 2 courses of treatment
- Change and percentage change in PBAC score over the course of the study. Specifically comparing the baseline menstrual cycle to the matching end-of-study period leading up to Week 18 and the end of treatment as well as comparing the baseline PBAC to the ODI time periods.
- Percentage change in UFSQOL Symptom Severity score (UFS-SSS) comparing Week 18 to Baseline (three month look back) and for the ODI.
- Percentage change in the individual UFS-SSS subscores
- Percentage change from baseline in total uterine fibroid volume measured by MRI

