8.2 Study Design

8.2.1 Overview of Study Design

This study is a phase 2 3-arm-study with a 36 week active dosing period. The study will be conducted in two stages.

[figure not shown]
[figure not shown]
[figure not shown]
In the first stage, women will undergo a baseline assessment period, with no treatment, until 15-20 days after the start of their second complete menstrual event. During this phase a pictorial blood loss assessment chart and daily diaries will be utilized. Used sanitary products from the first menstrual event will be collected and returned to the clinic for alkaline hematin assay. This assay will confirm subject eligibility (MBL must be 80 mL or greater by alkaline hematin assay for subjects to qualify).

In the second stage, subjects will be randomized into one of 3 arms in a 1-1-1 fashion. The start of the 18 week dosing period (Course 1) in this stage of the study should commence 15-20 days after the start of their first menses after Visit 2. Once active dosing is stopped, subjects will be followed until menses returns. The start of the second 18 week dosing period (Course 2) will commence 15-20 days after the start of their menses following withdrawal of drug after Course 1 has been completed. During the non dosing off-drug interval (ODI), subjects will continue to record study information in the daily paper diary and PBAC charts.

After end of dosing in Course 2, subjects will be followed through the subsequent recovery menses and for an additional 5 menstrual events, after which the subject may be offered the opportunity to enroll in an extension study. Subjects who fail to achieve amenorrhea may enroll in the extension study at Visit 19. Amenorrhea is defined as any 28-day period during treatment (not including the ODIs) without a bleeding score >1. Throughout the study women will record study information in the diary, PBAC and questionnaires as outlined in the study procedures.

In addition to the diary information, endometrial thickness will be recorded at screening and every month thereafter. Assessment of

trough levels of drug will be determined at every office visit during the first and second 18 week dosing periods.

The primary efficacy analysis will be conducted when all subjects complete the first cycle of treatment. A second analysis will summarize the subject's second treatment cycle which will be conducted after all subjects complete study treatment and follow-up.

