12.2.2.2 Secondary Endpoints

Percentage Change in PBAC scores

The percentage change in PBAC scores over each 28 day period for each menstrual cycle will be recorded and compared to baseline to determine onset of benefit. Additionally PBAC scores will be used to monitor the level of vaginal bleeding during the ODI and the time to return to baseline vaginal bleeding to determine duration of benefit during the five menstrual cycle follow-up after dosing Course 2.

Within treatment group paired t-tests will evaluate treatment effect. Pairwise comparisons of the treatment groups will be made using a two-sample t-test as well as compare the pooled Proellex doses to placebo. While the primary assessment will be after 18 weeks of treatment, summaries will be prepared for each of the other visits. If data are missing, a last observation carried forward procedure will be used, including the baseline, if necessary. Non-parametric methods will be employed as appropriate.

Percentage change in total and individual symptom severity scores for the UFS-SSS

The UFS-SSS is an 8 question symptom severity score and has been validated as a three month look back questionnaire. The survey will be administered at the baseline of each dosing course and at the end of each course. An analysis of UFS-SSS scores will compare the pooled Proellex dose results to the placebo group with a t-test. Pairwise comparisons of the treatment groups will be made using a two-sample t-test. Within group paired tests will also be used to assess treatment effect. Non-parametric methods will be employed as appropriate. The primary assessment will be based on Visit 12 (after 18 weeks of treatment). If data are missing, a last observation carried forward procedure will be used, including the baseline, if necessary.

Percentage Change in Uterine Fibroid Volume by MRI

The percent change from baseline in total uterine fibroid volume will be determined at the end of each 18 week dosing course and after the 6 months of recovery menses (Visit 24). This study will assess up to 3 fibroids present at baseline in each subject. The volume of these 3 fibroids will be summed to determine the total uterine fibroid volume at each assessment.

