## 3. STUDY DESIGN

### 3.1 OVERVIEW AND LENGTH OF STUDY

ZPV-201 is a phase 2 3-arm study with two 18-week dosing courses. The study will be conducted in 2 stages, with total study participation being approximately 18 months.

[figure not shown]
In the first stage, women will undergo a baseline assessment period with no treatment, until 15-20 days after the start of their second complete menstrual event. During this phase a pictorial blood loss assessment chart (PBAC) will be utilized as well as sanitary products collected from their first menstrual event, for alkaline hematin assay, to determine menstrual blood loss and confirm eligibility.

In the second stage, subjects will be randomized into one of 3 arms in a 1-1-1 fashion and receive two 18-week courses of treatment at their randomized dose level (6 mg, 12 mg, or placebo), separated by an off-drug interval (ODI). The start of the first 18-week course of treatment (Course 1) should commence 15-20 days after the start of their previous menses. Subjects should be instructed to continue vaginal dosing during their menses throughout the study and not to have sex or insert anything in the vagina for at least 1 hour after the capsule is inserted. Once dosing for Course 1 has stopped, subjects will be followed until menses return. The start of the second 18 week course of treatment (Course 2) will commence 15-20 days after the start of their menses following withdrawal of drug after Course 1 has been completed.

Efficacy will be assessed by: amenorrhea, PBAC scores, uterine fibroid symptoms-symptom severity score questionnaire (UFS-SSS), uterine fibroid volume, uterine volume, [REDACTED]

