### 6.8.3 UFS-SSS

The individual and combined symptom severity scores and percentage change from baseline will be summarized at the end of course 1 treatment, course 2 treatment, and each follow-up visit. Pairwise comparisons between treatment groups will be performed using t-tests and Wilcoxon rank-sum tests, as appropriate. Statistical significance of the change from baseline within treatment groups will be determined using a paired t-test or Wilcoxon signed-rank test, as appropriate.

[figure not shown]

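### The UFS-SSS has a three-month recall, so its off-drug-interval score and the first two to four follow-up scores mix on-drug and off-drug time and cannot by themselves support an off-drug claim

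*Protocol*

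**What the plan says.** - **Recall period.** Protocol 12.2.2.2 says the UFS-SSS "has been validated as a three month look back questionnaire".
- **Endpoint.** Protocol 8.1.2 lists percentage change in the score as a secondary endpoint, "comparing Week 18 to Baseline (three month look back) and for the ODI". The synopsis lists the same endpoint.
- **Survey times in the protocol.** Protocol 12.2.2.2: "The survey will be administered at the baseline of each dosing course and at the end of each course". No follow-up visit is named there. The primary UFS-SSS assessment is Visit 12, after 18 weeks of treatment.
- **Summary times in the SAP.** SAP 6.8.3 says scores and percentage change "will be summarized at the end of course 1 treatment, course 2 treatment, and each follow-up visit". It adds pairwise between-group tests and within-group tests of change from baseline, without saying which baseline or limiting the tests to particular visits. SAP 6.3 makes no multiplicity adjustment. Both SAP versions carry the same UFS-SSS text.
- **Length of the ODI.** Course 2 starts "15-20 days after the start of their menses following withdrawal of drug" (Protocol 8.2.1; SAP 3.1 agrees). Neither document says how long menses take to return.
- **Follow-up.** After Course 2, subjects are followed through six menses, and Protocol 8.2.3 gives durability of effect as the purpose. Protocol 12.2.2.2 assigns PBAC, scored over 28-day periods, to monitoring bleeding in the ODI and to duration of benefit.

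**The concern.** An off-drug result needs a measurement whose window lies off drug. A three-month recall meets that only about three months after the last dose. The one survey that the visible protocol text provides for the ODI is the Course 2 baseline, taken 15-20 days after menses return. Unless menses take a long time to return, that score covers the end of Course 1 dosing as well as the ODI. Surveys at the first menses after Course 2 would have the same problem.

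Randomization does not remove it. All arms recall a dosing period, but only the active arms recall one with active drug. If the drug relieves symptoms and the relief fades after withdrawal, the mixed scores lean toward the on-drug effect in those arms alone. A between-group difference could then be read as persisting benefit when part of it is memory of treatment. These comparisons are tested at the two-sided 0.05 level without adjustment.

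A second, conditional issue is the reference value. The protocol calls the pre-Course 2 survey a baseline, and SAP 6.8.3 says only change from baseline. A Course 2 change measured from a score that already contains treated time would come out too small.

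**Working it through.** The documents give no overlap figure to reproduce, so this is timeline arithmetic.

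**Inputs**
- Recall window L: three months (Protocol 12.2.2.2), taken as 91 days.
- Course length: 18 weeks = 18 × 7 = 126 days (SAP 3.1).
- End of ODI: g + 15 to g + 20 days after the last dose, where g is the number of days from last dose to start of menses (Protocol 8.2.1).
- g: not given. Assumed 28 days, range 14-56.
- Cycle length c after Course 2: not given. Assumed 28 days; 21 days tried as a short case.

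**Formula.** At t days after the last dose, on-drug share of recall = max(0, L − t) / L.

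**Step 1: Week 18 (Visit 12).** The 91-day window lies wholly inside the 126-day course. The share is 100% on drug, as intended, so the primary UFS-SSS assessment is not affected.

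**Step 2: end of ODI (Course 2 baseline).**

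| g (days) | t = g + 15 to g + 20 | On-drug days of 91 | Share |
|---|---|---|---|
| 14 | 29-34 | 62-57 | 68-63% |
| 28 | 43-48 | 48-43 | 53-47% |
| 42 | 57-62 | 34-29 | 37-32% |
| 56 | 71-76 | 20-15 | 22-16% |

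The window is fully off drug only if g is at least 91 − 20 = 71 days (Course 2 started on day 20) or 91 − 15 = 76 days (started on day 15).

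**Step 3: follow-up after Course 2.** For a score at the start of menses k, t = g + c(k − 1).

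| g, c (days) | Menses 1 | 2 | 3 | 4 | 5-6 |
|---|---|---|---|---|---|
| 28, 28 | 69% | 38% | 8% | 0% | 0% |
| 14, 28 | 85% | 54% | 23% | 0% | 0% |
| 56, 28 | 38% | 8% | 0% | 0% | 0% |
| 14, 21 | 85% | 62% | 38% | 15% | 0% |

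Example, first row: t = 28, 56, 84, 112, so the shares are 63/91, 35/91, 7/91 and 0.

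**Step 4: survey times side by side.** Protocol 12.2.2.2 places the survey at the start and end of each course. SAP 6.8.3 summarizes it at the end of each course and at "course 2 treatment, and each follow-up visit". On the visible text, the SAP uses follow-up scores for which the protocol section names no administration.

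**The case against.** The case against has real force, and most of it limits the point rather than removing it.

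- **A reader might infer that every follow-up score is affected.** The arithmetic does not support that. From about the fourth menses (the fifth in the shortest case tried) the window is entirely off drug, including the sixth menses, which matters most for durability.
- **A reader might infer that the plan's durability conclusion rests on the UFS-SSS.** It does not: Protocol 12.2.2.2 gives duration of benefit to PBAC. But the UFS-SSS for the ODI is still a named secondary endpoint, and it will be reported and tested.
- **A reader might take the on-drug share as the fraction of symptom return that is concealed.** That would need an on-drug benefit that wanes and recall that weights all 91 days equally. The documents establish neither. If recall favors recent weeks, the distortion is smaller than the share suggests.
- **A reader might infer that Course 2 changes will be understated.** No visible text computes change from the Course 2 baseline. What stands is that SAP 6.8.3 does not say which baseline applies.
- **The visit schedule and procedures are not visible in the public copy.** A different recall instruction at off-drug visits cannot be excluded. The only recall period for which the protocol claims validation is three months.

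**Conclusion.** The point holds for the ODI score and for early follow-up. With return of menses at 14-56 days, about 68% down to 16% of the recall at the end of the ODI is on drug, and only a return at about 71-76 days or later would clear it. After Course 2, at day-28 menses and 28-day cycles, the first three menses carry about 69%, 38% and 8%, and later ones none.

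These are shares of recall time and rest on assumed values for g and c. They are not estimates of bias. The direction is conditional: if treatment improves symptoms and the benefit wanes, the affected scores may overstate persisting benefit in the active arms and not in placebo. How much cannot be derived from the documents. The point deserves correction because the plan as written reports and tests an off-drug endpoint that the instrument cannot measure at that time.

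**What to change.** In SAP 6.8.3:

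1. State that all UFS-SSS changes are computed from the pre-Course 1 baseline.
2. Base any off-drug or durability statement only on scores taken at least 91 days after the last dose, judged by each subject's own dates rather than by visit number.
3. Report ODI and earlier follow-up scores as mixed on/off-drug, and rely on PBAC, which is already planned, as the ODI measure.
4. Reconcile the survey times in Protocol 12.2.2.2 with the follow-up summaries in SAP 6.8.3.

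Items 1-3 are SAP wording. Item 4 is wording only if the survey is in fact given at late follow-up visits. If it is not, item 2 leaves no UFS-SSS score for an off-drug statement, and the SAP should say so.

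The price is that no UFS-SSS off-drug claim can be made for the ODI. Late visits also need care: subjects who fail to achieve amenorrhea may enter the extension at Visit 19 (Protocol 8.2.1), so the numbers remaining should be shown by arm.

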12.3 General Statistical Issues

A Statistical Analysis Plan (SAP) will be finalized prior to unblinding the study. For the efficacy variables a last observation forward approach will be used to impute missing data to generate a complete ITT data. If there are no post-baseline efficacy data then a value of no change will be imputed for the missing efficacy measure. Statistical significance will be declared if the two-sided p-value is ≤ 0.05 .

13. ETHICS

13.1 Subject Information and Consent

A properly executed, written informed consent in compliance with Food and Drug Administration (FDA) regulations and Good Clinical Practice (GCP) guidelines will be obtained from each subject prior to entering the study or performing any unusual or non-routine procedure that involve a risk to the subject. The Principal Investigator will submit a copy of the informed consent document to the Institutional Review Board for review and approval before research subjects are enrolled. The Principal Investigator will provide a copy of the signed informed consent to the subject and the original will be maintained in the subject's medical record.

13.2 Institutional Review Board

The Principal Investigator will provide the Institutional Review Board with all requisite material, including a copy of the informed consent. The study will not be initiated until the IRB provides written approval of the protocol and the informed consent and until approved documents have been obtained by the Principal Investigator and copies received by the Sponsor. Appropriate reports on the progress of this study by the Principal Investigator will be made to the Institutional Review Board and the Sponsor in accordance with the applicable government regulations and in agreement with the policy established by the Sponsor.

13.3 Monitoring Case Report Forms

Repros Therapeutics Inc. or their designee will monitor all aspects of the study with respect to current GCP and standard operating procedures for compliance with applicable federal regulations. These individuals will have access to all records necessary to ensure integrity of the data and will periodically review progress of the study with the Principal Investigator.

13.4 Study Record Retention

In accordance with FDA regulations and GCP guidelines, all study-related documentation shall be retained by the Principal Investigator for a minimum of 2 years after FDA approval of telapristone acetate or clinical development has been terminated. At that time, the Principal Investigator will contact Repros Therapeutics Inc. regarding further disposition of the study records and comply with instructions.

13.5 Data Quality Assurance

All data recorded during the study will be available for audit against source data and for compliance with GCP and specific protocol requirements. Monitoring of the study progress and conduct will be ongoing. The Principal Investigator will be responsible for the following:

1. Monitoring study conduct to ensure that the rights of subjects are protected;

2. Monitoring study conduct to ensure trial compliance with GCP guidelines; and
3. Monitoring accuracy, completion and verification from source documents of study data.

13.6 Confidentiality

All information provided to the Principal Investigator by Repros Therapeutics Inc. or their designees including non-clinical data, protocols, CRFs and verbal and written information will be kept strictly confidential and confined to the clinical personnel involved in conducting the study. It is recognized that this information may be released in confidence to the IRB. In addition, no reports or information about the study or its progress will be provided to anyone not involved in the study other than to Repros Therapeutics Inc. or their designees or in confidence to the IRB, except if required by law.

13.7 Publications

Following completion of the study, the data from the entire study or from subsets of the study may be considered for reporting at a scientific meeting or for publication in a scientific journal, in which case Repros Therapeutics Inc. will be responsible for these activities and will work with the Principal Investigator to determine how the manuscript is written and edited, the number and order of authors, the publication to which it will be submitted and other related issues.

[figure not shown]
14. INVESTIGATOR'S STATEMENT

[figure not shown]
I have reviewed the ZPV-201 protocol and Investigator Brochure and agree to conduct this study as outlined in the protocol and in compliance with ICH/GCP Guidelines.

[figure not shown]
Investigator

[figure not shown]
Date

[figure not shown]
Printed name

[figure not shown]

[figure not shown]

[figure not shown]

[figure not shown]

[figure not shown]

[figure not shown]

ZPV-201 Amendment 4 Protocol Summary of Changes

Protocol Title: A Phase 2, Multi-Center, Parallel Design, Randomized, Double-Blind Study to Evaluate the Safety and Efficacy of 6 and 12 mg Proellex® (Telapristone Acetate) Administered Vaginally in the Treatment of Premenopausal Women with Confirmed Symptomatic Uterine Fibroids

Changes From: From Protocol Amendment 3 dated April 8, 2016 To: Protocol Amendment 4 dated June 20, 2016

Reason for Amendment: Addition of MRI at Visit 24, addition of requirements for enrollment in Extension Study

Changes to Protocol: Significant changes to the protocol are listed below.

SECTION	CHANGED FROM	CHANGED TO	REASON FOR CHANGE
Protocol Synopsis-Study Design and Duration of Treatment	After completion of stage 2 dosing (Courses 1 and 2), subjects will be followed through the subsequent 6 menses (recovery menses plus an additional 5 menstrual events). In the event that a subject's menstrual bleeding returns to $\geq 80\text{mL}$ (assessed by alkaline hematin assay) at the end of this period, the subject may be offered the opportunity to enroll in an extension study.	After completion of stage 2 dosing (Courses 1 and 2), subjects will be followed through the subsequent 6 menses (recovery menses plus an additional 5 menstrual events), after which (at Visit 24) the subject may be offered the opportunity to enroll in an open-label extension study. Subjects who fail to achieve amenorrhea may enroll in the extension study at Visit 19. Amenorrhea is defined as any 28-day period during treatment (not including the ODIs) without a bleeding score >1 .	Change in study design
8.2.1 Overview of Study Design	After end of dosing in Course 2, subjects will be followed through the subsequent recovery menses and for an additional 5 menstrual events. In the event that a subject's menstrual bleeding returns to $\geq 80\text{ mL}$ (assessed by alkaline hematin assay) at the end of this period the subject may be offered the	After end of dosing in Course 2, subjects will be followed through the subsequent recovery menses and for an additional 5 menstrual events, after which the subject may be offered the opportunity to enroll in an extension study. Subjects who fail to achieve amenorrhea may enroll in the extension study at Visit 19.	Requirements for roll-over into Extension Study added

SECTION	CHANGED FROM	CHANGED TO	REASON FOR CHANGE
	opportunity to enroll in an extension study.	Amenorrhea is defined as any 28-day period during treatment (not including the ODIs) without a bleeding score >1.	
8.2.3 Randomization and Blinding	After the second treatment course is completed the subjects will be followed for 6 menstrual events to determine durability of effect of treatment. If subjects return to a MBL score of ≥80 mL at the end of this period, assessed by alkaline hematin assay, they may be offered the opportunity to enroll in an extension study.	After the second treatment course is completed the subjects will be followed for 6 menstrual events to determine durability of effect of treatment, after which they may be offered the opportunity to enroll in an open-label extension study. Subjects who fail to achieve amenorrhea may enroll in the extension study at Visit 19. Amenorrhea is defined as any 28-day period during treatment (not including the ODIs) without a bleeding score >1.	Requirements for roll-over into Extension Study added

SECTION	CHANGED FROM	CHANGED TO	REASON FOR CHANGE
	[REDACTED]	[REDACTED]	Study changed
	[REDACTED]	[REDACTED]	[REDACTED]
	[REDACTED]	[REDACTED]	[REDACTED]
12. STATISTICAL METHODS 12.2.2.2 Secondary Endpoints	Percentage Change in Uterine Fibroid Volume by MRI The percent change from baseline in total uterine fibroid volume will be determined at the end of each 18 week dosing course.	Percentage Change in Uterine Fibroid Volume by MRI The percent change from baseline in total uterine fibroid volume will be determined at the end of each 18 week dosing course and after the 6 months of recovery menses (Visit 24).	New procedure added
	[REDACTED]	[REDACTED]	[REDACTED]
	[REDACTED]	[REDACTED]	[REDACTED]
	[REDACTED]	[REDACTED]	[REDACTED]

Charts and footnotes were updated to reflect the changes above.
